2.5 SAFETY MONITORING

Prior studies suggested that hypotension and methemoglobinemia may occur with the use of sodium nitrite. The study treatment of inhaled nitrite will be used safely with careful monitoring and prompt discontinuation of the study treatment in response to systemic hypotension with definitions of dose limiting toxicity. The presence of severe DLT deemed to be study-drug related will lead to a discontinuation of the study treatment.

Following study drug treatment, subjects will be evaluated as an outpatient at the clinic on Day 42 (+/- 5 day window). Interval study visits (days 7, 14 and 28) have been included in the study design to ensure subject safety. Subjects will be followed for evidence of acute or delayed adverse effects from the study treatment and to assess their clinical status. All adverse events experienced by subjects will be collected from beginning of visit 1 through final study visit. Study subjects will be routinely questioned about adverse events at study visits. The study investigators will evaluate all subject reported and observed AEs. All untoward medical occurrences observed in subjects receiving the study drug will be recorded on the participants' adverse event worksheets by the study coordinator under the supervision of the principal investigator. AEs occurring pre-treatment, during active treatment and post-treatment will be summarized separately. Subjects continuing to experience toxicity at the off study visit may be

contacted for additional assessments until the toxicity has resolved or is deemed irreversible. If possible, symptoms should be managed symptomatically. In the case of toxicity, appropriate medical treatment should be used.

In addition to these formal evaluations, subjects will be encouraged to immediately contact the study investigator and/or the study coordinator with questions, concerns, or to report new symptoms that occur during their study participation. If appropriate, based upon the evaluation, medical treatments will be provided to subjects, including appropriate referral to physicians or other services at the UPMC.

2.6 STOPPING RULES

Two distinct scenarios in which subjects must be removed from the study are anticipated.

First, the subject experiences a CF respiratory exacerbation marked by a persistent drop in FEV1 >15% that is not temporally associated with nebulized sodium nitrite administration. The drop in FEV1 would be seen on the first set of spirometry at a visit, prior to dosing of nebulized sodium nitrite for that day. In this case, subjects will be removed from the study and referred to their pulmonologist for treatment of the CF respiratory exacerbation.

Drop in FEV1 >15% on the first set of spirometry, prior to drug administration, on any study visit when compared with baseline spirometry collected at screening.

In the second scenario, nebulized sodium nitrite is associated with a dose-dependent intolerance that will be seen at the dose escalation visit 2, or after receiving the first dose of drug on visit 1. Specific intolerances of concern are acute bronchospasm, hypotension or methemoglobinemia. In this case, if any one of the below occurs at the 45 mg dose, subject will be removed from the study; if any occur at the 90 mg dose, the subject will return to the previously tolerated dose of 45 mg.

Specific criteria for dose-dependent intolerance are:

Decrease in FEV1 by >15% between measurements on an individual study visit.

A decrease in systolic BP > 40 mmHg drop from pre-dose baseline or to <80mmHg and symptomatic.

SaO₂ drop below 88% and symptomatic or SaO₂ desaturation > 5% from baseline and symptomatic

A single occurrence of venous methemoglobin level >5%

Any serious adverse event thought to be possibly related to the study treatment

2.7 STUDY INVESTIGATIONAL THERAPY SUPPLIES

2.8.1 Formulation and Packaging

Formulation:

The active ingredient of the Sodium Nitrite Inhalation Solution (nebulized sodium nitrite Inhalation Solution) is sodium nitrite in a sterile aqueous solution approved for intravenous use. It is packaged at a 30 mg/mL in 10ml vials.

Packaging:

Vials will be purchased from Hope Pharmaceuticals and patients will withdraw the appropriate volume using a 3 mL sterile syringe with needle and place in nebulizer. Study subjects have extensive experience administering maintenance CF medications using this technique.

2.7.2 Availability

Nebulized sodium nitrite will be purchased from Hope Pharmaceuticals. We will ensure that enough compound is on site to complete the study prior to enrolling any individual subject

2.7.3 Preparing and Dispensing

The study drug will dispensed by the research pharmacist and the research coordinator will provide instructions for withdrawing the appropriate volume via a syringe with needle and delivering to the nebulizer device.

2.7.4 Drug Administration

The route of administration is by nebulization. It is anticipated that each nebulization will take approximately 10 – 15 minutes to deliver the dose. All doses specified in the protocol are the amounts of nebulized sodium nitrite placed into the nebulizer cup. We will be using Aerogen Solo nebulizers, as was done in the study by Simon, *et al* (17).

2.8 STUDY INVESTIGATIONAL THERAPY STORAGE

The investigational drug will be kept in its original packaging and stored in a locked, secure area at controlled room temperature (20 – 25° C) with the investigation drug services (IDS). The temperature of the storage area must be monitored to ensure compliance with required temperatures. A temperature log will be maintained to make certain that the drug supplies are stored at the correct temperature at all times maintained by IDS. Access to and administration of the investigational drug will be limited to the study investigators and authorized research staff. Study drugs may only be dispensed to subjects enrolled in this study.

2.9 STUDY INVESTIGATIONAL THERAPY ACCOUNTABILITY

The study investigators or the study coordinator will document the amount of study drugs dispensed and/or administered to subjects. The study drugs accountability records will be maintained throughout the course of the clinical trial by IDS. Any discrepancies in drug supplies will be noted and explained.

2.10 STUDY PROCEDURES

Screening: Potential subjects will be recruited from the CF Center at Children's Hospital of Pittsburgh and/or the UPMC Comprehensive Lung Center (CLC). In these locations, individuals with CF are followed on a routine basis, and well known to one or more of the study investigators. After informed consent is obtained, screening evaluations, including urine

pregnancy test (only on females of childbearing potential), physical examination, medical history, and clinical laboratory assessments, will be conducted to determine study eligibilities during a routine clinic visit. In addition, vital signs (pulse, non-invasive blood pressure measurement, temperature, respiratory rate and oxygen saturation) will be performed and baseline spirometry will be obtained. Screening is further discussed in Section 2.2.1.

Spirometry: FEV₁ will be measured with a handheld spirometer as the primary endpoint. Spirometry is performed for patients with CF at every outpatient visit, thus the subjects will have had experience performing spirometry since they were children. A baseline spirometry will be done as well as spirometry at 30 and 120 minutes following nebulization of nebulized sodium nitrite on days 0 and 7. Spirometry will also be performed at subsequent visits on days 14, 28 and 42.

Sputum Induction: Sputum induction will be performed per the CF Foundation Therapeutic Development Network SOP. See detailed protocol in appendix. In brief, the Sputum Induction (SI) procedure consists of four 3-minute cycles during which the participant breathes aerosolized 3% hypertonic saline and then expectorates sputum into a sample container. The participant's peak flow is monitored at the end of each cycle. As long as the peak flow remains $\geq 80\%$ of pre-induction baseline, the cycle is repeated four (4) times. An optional fifth 3-minute cycle may be employed for those participants who have not yet expectorated an adequate sample and are tolerating the procedure. The complete procedure includes several preparatory steps, discharge monitoring, and clean up. For the participant, the entire sputum induction procedure from the time of initial assessment (vital signs and peak flow) to the end of the induction with associated monitoring is expected to last approximately 25-35 minutes. Total saline inhalation time should not exceed 15 minutes.

If subjects spontaneously expectorate, then sputum induction will not be done. After sputum induction, subjects will wait a minimum of 30 minutes prior to nebulization of nebulized sodium nitrite because sputum induction can cause temporary bronchoconstriction and this might confound the safety assessment of nebulized sodium nitrite. The amount of wait time will be determined by the physician investigator at the time of visit. Sputum induction will be done on Study days 0, 14, 28, and 42. If no further administration of nebulized sodium nitrite is planned during the visit (Days 14, 28, and 42), subjects may leave after sputum induction if they are not symptomatic.

Nebulization of Drug: nebulized sodium nitrite will be nebulized via electronic nebulizer with direct observation by a study physician or nurse coordinator on day 0, and at dose escalation by a study physician or nurse coordinator on day 7 in the CTRC, CHP or an Emphysema Research Center room in Montefiore. Subsequent doses will be self-administered by the subjects two times daily at home.

CFQ-R Questionnaire: Subjects will complete this standard and validated questionnaire on paper. Results of the CFQ-R will be confidentially stored electronically. Original paper will be maintained and stored in the locked Pulmonary Medicine Allergy and Immunology office.

NIOX device: Subjects exhale slowly through the device as guided by a small video screen with a smiling cloud icon. Disposable filters are used for each subject to minimize infection control concerns with the device. NIOX data will be recorded on days 0, 7 and 28.

Phlebotomy: Blood will be drawn by trained personnel at the screening visit (and day 0 if labs require repeating). Peripheral blood for confirmatory methemoglobin level will be obtained if percutaneous methemoglobin levels exceed 5%.

Vital sign measurements: Pulse, systemic blood pressure, temperature, respiratory rate and pulse oximetry will be measured noninvasively by trained study personnel using standard clinical equipment. All these values will be measured on screening visit and days 0, 7 and 42 (exit exam). On days 0 and 7 when nebulized sodium nitrite is being administered with observation, percutaneous measurements of oxygen saturation and methemoglobin levels will be measured for two hours after delivery. Noninvasive systemic blood pressure measurements will be taken every 15 minutes for the first two hours.

Subjects will be monitored carefully for adverse events, laboratory test abnormalities, and changes in vital signs. Adverse experiences will be evaluated according to criteria outlined in the NCI Common Terminology Criteria for Adverse Events (CTCAE), version 4.0

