Within the lung, the chemistries of nitrite and nitric oxide (NO) are closely related. Nitrite is reduced to NO both enzymatically and nonenzymatically. NO is formed when nitrite reacts with metal containing proteins such as hemoglobin and cytochrome c oxidase (mitochondrial complex 4)(10). These reactions are influenced by both pH and oxygen tension, and occur more rapidly under acidic conditions with a low oxygen tension, such as those found in the CF lung (6). NO has a biologic half-life of milliseconds and is the principle regulator of pulmonary vascular tone. With a half life of 51 minutes when delivered IV (and potentially longer when inhaled), nitrite can be viewed as a long acting source of NO(11, 12). In addition to its role as a vasodilator, nitrite plays a role in innate immunity. In the epithelium NO is produced by inducible nitric oxide synthetase (iNOS) from L-Arginine. In the healthy lung, both the airway epithelium and immune cells produce NO. However, in CF the airway epithelium expresses much less iNOS leading to decreased exhaled nitric oxide (13). Low exhaled nitric oxide levels are correlated with worse lung function as well as *P. aeruginosa* colonization in CF (14). Because NO has strong antimicrobial effects, low NO levels in the airway may contribute to the susceptibility to bacterial colonization in CF. Nitrite has the theoretical added benefit of restoring normal airway NO levels in patients, such as those with CF, who have an endogenous NO production defect. The antimicrobial activity of nitrite derives from its ability to inhibit bacterial respiration(7, 15). The precise molecular targets are an area of active investigation, but nitrite can inactivate heme-containing proteins (such as cytochrome c oxidases), disrupt iron-sulfur containing proteins (such as NADH dehydrogenase and succinate dehydrogenase), and S-nitrosate redox active cysteine residues impairing protein function (16). Nitrite was initially proposed as an inhaled antimicrobial agent in 2006 by [name] group, however compound to perform clinical trials was not available until recently and preclinical safety data was not previously available.

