
1.4 SIGNIFICANCE

Chronic airway infections with multi-drug resistant Gram-negative organisms are common in patients with structural lung diseases, particularly CF but also including those with non-CF bronchiectasis, COPD, following lung transplant, and those with chronic airway hardware such as tracheostomies. The current FDA approved inhaled antibiotics are limited to tobramycin and aztreonam, to which many organisms are resistant. We hypothesize that inhaled nitrite provides an innovative therapeutic approach for patients with chronic airway infections because:

1. Nitrite has broad antimicrobial activity against all organisms tested, including respiratory isolates of *Burkholderia cepacia* complex, *Staphylococcus aureus*,

Achromobacter complex, and *Klebsiella pneumoniae*(5, 9). This study will provide proof-of-concept efficacy data that nitrite inhibits bacterial growth.

2. The antimicrobial activity of nitrite increases under anaerobic and acidotic conditions such as those found in the CF airway. Both low pH and oxygen tension decrease the activity of many antibiotics.
3. This study will provide evidence that nebulize nitrite can reconstitute the NO deficiency found in CF.
4. The results obtained in this study will lay the groundwork for future large scale clinical trials needed to determine the efficacy of inhaled nitrite as an antibiotic in patients with cystic fibrosis and other patient populations with chronic airway infections.

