Experimental Procedures (visit 1/day 0 (+/- 1day)): This visit will take approximately 5 hours. Subjects will arrive and complete the CFQ-R CF Questionnaire. Vital signs will be recorded and a physical examination performed, subjects will provide a sputum sample if able, and complete an oral wash specimen. The fractional excretion of nitric oxide (FENO) will be measured using a NIOX device, and baseline spirometry will be obtained. If subjects are unable to spontaneously expectorate sputum, then sputum induction will be done, followed by at least a 30 minute observation period because sputum induction is associated with temporary bronchoconstriction which might confound further measurements. The observation period will be omitted in subjects that spontaneously expectorated sputum. Next, an electronic nebulizer will be used to deliver 45 mg of nebulized sodium nitrite. Subjects will be monitored closely for the next two hours, including percutaneous measurements of oxygen saturation and methemoglobin levels, recorded at minutes 15, 30, 60 and 120, and noninvasive systemic blood pressure measurements every 15 minutes. Spirometry will be repeated at 30 and 120 minutes following nebulized sodium nitrite administration. If percutaneous methemoglobin measurements exceed 5%, they will be confirmed by venous blood measurement. If nebulized sodium nitrite is tolerated, then the subject will be dispensed an 8 day supply of 45 mg nebulized sodium nitrite dosed two times daily and discharged from the CTRC, CHP or the Emphysema Research Center in Montefiore. If the 45mg dose of nebulized sodium nitrite is not tolerated, the subject will be observed until stable and then discharged from the CTRC, CHP or the Emphysema Research Center in Montefiore.

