Experimental Procedure (visit 2/day 7 (+/- 1day)): This visit will take approximately 5-7 hours. Subjects will arrive and complete the CFQ-R CF Questionnaire. FENO will be measured as above. If the subject had no serious adverse events for the first seven days of the 45 mg dose of nebulized sodium nitrite, and has stable systemic blood pressure and FEV₁ on presentation to the Day 7 visit, an electronic nebulizer will be used to deliver 90 mg of nebulized sodium nitrite. Subjects will be monitored closely for the next two hours, including percutaneous measurements of oxygen saturation and methemoglobin levels, recorded at minutes 15, 30, 60 and 120, and noninvasive systemic blood pressure measurements every 15 minutes. If percutaneous methemoglobin measurements exceed 5%, they will be confirmed by venous blood measurement. Spirometry will be repeated at 30 and 120 minutes following nebulized sodium nitrite administration. If nebulized sodium nitrite is tolerated, then the subject will be dispensed an 8 day supply of 90 mg nebulized sodium nitrite dosed two times daily and discharged from the CTRC, CHP or the Emphysema Research Center in Montefiore. If the 90 mg dose of nebulized sodium nitrite was not tolerated, the subject will be observed. If FEV₁ returns to baseline in 4 hours and subject's SaO₂ is not greater than 5% drop from baseline and systolic BP is not greater than 40 mm Hg drop from pre-dose baseline, the subject will be re-challenged at this visit with a 45 mg dose of nebulized sodium nitrite and the observation protocol of blood pressure measurements, spirometry and percutaneous oxygen saturation measurement will be repeated.

Experimental Procedures (visit 3/day 14(+/- 1day)): This is a safety and tolerability visit and will take approximately 1 hour. Subjects will complete the CFQ-R and spirometry. An oral wash will be collected, and then a sputum sample will be collected. If the subject cannot spontaneously expectorate, then sputum induction will be done. The subject will then be discharged with a 15 day supply of nebulized sodium nitrite.

Experimental Procedures (visit 4/day 28(+/- 1day)): This visit will take approximately 1.5 hours. Subjects will complete the CFQ-R and spirometry. Expectorated or induced sputum will be collected, an oral wash will be collected, and FE_{NO} measured as above. Sputum will be used to measure nitrite concentration and quantitative bacterial load.

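### No exhaled NO reading follows an observed dose, and on-treatment exhaled NO and sputum nitrite have no set or recorded time since the last home dose

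*Combined protocol and SAP*

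**What the plan says.** FENO and sputum nitrite are secondary endpoints (Section 2.13.2), and exhaled NO is one of the three effects that Aim 2 explores (Section 1.2). Section 1.4 goes further: "This study will provide evidence that nebulize nitrite can reconstitute the NO deficiency found in CF".

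The timing has to be pieced together from several places:

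- **Days (Section 2.10).** "NIOX data will be recorded on days 0, 7 and 28". Sputum is taken on Days 0, 14, 28 and 42.
- **Day 0 (Section 2.2.1, visit 1).** "subjects will provide a sputum sample if able", then "The fractional excretion of nitric oxide (FENO) will be measured using a NIOX device, and baseline spirometry will be obtained". Induction follows for those who could not expectorate. Only after that: "Next, an electronic nebulizer will be used to deliver 45 mg of nebulized sodium nitrite".
- **Day 7 (visit 2).** On arrival, "FENO will be measured as above"; the observed 90 mg dose comes later in the narrative. No sputum is taken.
- **After the observed doses on Days 0 and 7.** Oxygen saturation, methemoglobin, blood pressure and spirometry (at 30 and 120 minutes) are measured over two hours. FENO is not listed.
- **Day 28 (visit 4).** FENO and sputum are each taken once: "Sputum will be used to measure nitrite concentration and quantitative bacterial load". Section 2.10 plans no clinic dose that day.
- **Home dosing (Section 2.10).** Self-administered twice daily. No clock time is specified or recorded for the dose before a visit.

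The schedule in Section 2.11 gives methemoglobin dose-relative times (pre-dose and about 5, 15, 30, 60 and 120 minutes) but gives none for FENO or sputum.

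**The concern.** Section 1.3.1 describes NO as lasting milliseconds and nitrite as its longer-acting source. It puts the half-life of nitrite in these terms: "With a half life of 51 minutes when delivered IV (and potentially longer when inhaled". On that account, an exhaled NO reading depends on how much nitrite is left when the subject exhales. A schedule meant to show that the drug restores airway NO would then need at least one reading at a known, short time after a dose.

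The schedule has none. If FENO on Day 7 or 28 is unchanged from Day 0, there are two explanations: nitrite does not raise airway NO, or it does and the reading came too late. The data as collected could not separate them. An on-treatment sputum nitrite value has the same ambiguity. There is no control arm, and Section 2.15 has no analysis of either endpoint that could bring in time since dose.

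**Working it through.** The plan derives no figure for FENO or sputum nitrite. Its only power statement concerns discontinuation for FEV₁ decline and has no bearing here. The check is therefore of the schedule, followed by an illustration.

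**Step 1. Each sample against the nearest dose**

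| Day | FENO | Sputum nitrite | Relation to dose |
|---|---|---|---|
| 0 | yes | yes | before any drug |
| 7 | yes | no | before the observed 90 mg dose (inferred from narrative order); time since last home dose not set |
| 14 | no | yes | time since last home dose not set |
| 28 | yes | yes | time since last home dose not set |
| 42 | no | yes | about 14 days after treatment ends |

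No FENO reading follows an observed dose. FENO and sputum nitrite coincide only on Days 0 and 28.

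**Step 2. How much the interval could matter**

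Inputs:

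- Half-life of 51 minutes, intravenous (Section 1.3.1).
- Assumed longer inhaled half-lives of 102 and 204 minutes (two and four times 51), because the protocol says the inhaled value may be longer but gives no number.
- Assumed exponential decay of the last dose.
- Assumed interval of 1 to 12 hours, taking evenly spaced twice-daily doses.

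Formula: fraction remaining = 0.5^(t / half-life).

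- 51 min: 0.5^(60/51) = 0.442; 0.5^(120/51) = 0.196; 0.5^(720/51) = 0.000056.
- 204 min: 0.5^(60/204) = 0.816; 0.5^(120/204) = 0.665; 0.5^(720/204) = 0.087.

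| Half-life | 1 h | 2 h | 4 h | 8 h | 12 h |
|---|---|---|---|---|---|
| 51 min (IV, from the protocol) | 44% | 20% | 3.8% | 0.15% | 0.006% |
| 102 min (assumed) | 67% | 44% | 20% | 3.8% | 0.75% |
| 204 min (assumed) | 82% | 67% | 44% | 20% | 8.7% |

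Even at the longest assumed half-life, a 1-hour and a 12-hour sample differ about ninefold in nitrite remaining (81.6 / 8.66 = 9.4).

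**Step 3. What the schedule can and cannot distinguish**

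- A rise on Day 7 or 28 over Day 0 is visible as a within-subject change, although without a control arm.
- A null change is compatible both with no effect and with a late reading.
- The response in the hours after a dose is not observed at all.

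**The case against.** The strongest reply is that this is a Phase I/II safety study. FENO is one of six secondary endpoints, no dosing, stopping or sample-size rule rests on it, and an acute FENO curve is a design preference. That sets the priority of the point but does not remove it, because Section 1.4 promises evidence on NO reconstitution and the subjects are already on site for two hours after the dose.

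Several stronger readings are tempting, and the reply defeats them:

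- **That the trial cannot show any NO effect.** Day 0 is a drug-free baseline and the later readings fall during, or at the end of, twice-daily dosing, so a persistent rise could be detected.
- **That sputum nitrite is never timed.** Day 0 is pre-dose and Day 42 is off drug. Only Days 14 and 28 are untimed.
- **That Aim 2 as a whole fails.** The aim also covers lung function and bacterial burden. Only its exhaled-NO part is affected here.
- **That percent of dose remaining is the expected FENO signal.** The documents give no airway half-life and no relation between nitrite and FENO. Section 1.3.3 estimates an initial 82 mM after 80 mg; 3.8% of that at 4 hours is still about 3 mM (82 × 0.038 = 3.1), and nothing says whether that would leave FENO unchanged.
- **That test order biases the comparison.** FENO precedes spirometry in the visit 1 text and is listed after it for visit 4, but the visit 4 list is not clearly a prescribed sequence. The documents do not say that spirometry or sputum collection alters FENO. The protocol's caution about induction confounding later measurements concerns bronchoconstriction.

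**Conclusion.** The point holds in limited form. As scheduled, the study does not measure the acute NO response to nitrite, and a null on-treatment change in FENO could not be told from a late reading. On-treatment sputum nitrite is likewise hard to interpret. This weakens the NO-reconstitution claim in Section 1.4 and the exhaled-NO part of Aim 2, with no effect on the primary endpoint or on safety monitoring.

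The size is illustrative: between 1 and 12 hours after a dose, the nitrite remaining falls from 44% to 0.006% at 51 minutes, or from 82% to 8.7% at 204 minutes. This rests on exponential decay, on an intravenous half-life or an assumed multiple of it, and on evenly spaced home doses. It describes nitrite, not FENO.

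A reader might also call the existing readings trough values. They are not shown to be: Day 0 precedes treatment, and Days 7 and 28 have no set interval. The pre-dose position on Day 7 is itself an inference, since the schedule in Section 2.11 gives FENO no time. This is a cheap improvement to a secondary endpoint.

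**What to change.** 1. Add a FENO reading just before the existing 30-minute and/or 120-minute post-dose spirometry on Days 0 and 7, and give FENO dose-relative times in Section 2.11, as is done for methemoglobin.
2. Record the clock time of the last home dose on Days 7, 14 and 28.
3. Take Day 28 FENO and sputum at one prespecified interval after the last dose. If that is impractical, prespecify an analysis that uses the recorded time since dose.
4. Keep the order of the pre-dose tests the same across visits where feasible. A post-dose FENO on Days 0 and 7 will necessarily follow the baseline tests.

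The cost is up to four more exhalations per subject, of about 10 seconds each (Section 2.12.6), on a device already in use, plus one more recorded time at three visits. The real inconvenience is arranging the Day 28 appointment around the home dose. No extra visit, staff or device is needed.
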